9.3 Pregnancy and Lactation Reporting

If a pregnancy occurs in a female subject, or female partner of a male subject, while the subject is taking protocol-required therapies report the pregnancy to Amgen as specified below.

In addition to reporting any pregnancies occurring during the study, investigators should monitor for pregnancies that occur after the last dose of protocol-required therapies through 1 month after the end of IP.

The pregnancy should be reported to Amgen's global Pregnancy Surveillance Program within 24 hours of the investigator's knowledge of the event of a pregnancy. Report a pregnancy on the Pregnancy Notification Worksheet (Appendix C). The Pregnancy Surveillance Program (PSP) will seek to follow the pregnant woman throughout her pregnancy and her baby up to 12 months after birth.

If a lactation case occurs while the female subject is taking protocol-required therapies report the lactation case to Amgen as specified below.

Page 43 of 66

In addition to reporting a lactation case during the study, investigators should monitor for lactation cases that occur after the last dose of protocol-required therapies through 1 month after last dose of IP.

Any lactation case should be reported to Amgen's global Lactation Surveillance Program (LSP) within 24 hours of the investigator's knowledge of event. Report a lactation case on the Lactation Notification Worksheet (Appendix C).

10. STATISTICAL CONSIDERATIONS

10.1 Study Endpoints, Analysis Sets, and Covariates

10.1.1 Study Endpoint

Primary Endpoint: Subject incidence of treatment-emergent adverse events

10.1.2 Analysis Sets

The analysis set will include all subjects who enrolled in the study and received at least 1 dose of the investigational product (darbepoetin alfa).

10.1.3 Covariates and Subgroups

No planned subgroups or covariates will be used in the analysis of the study.

10.2 Sample Size Considerations

No sample size estimation is required. The number of subjects will be determined by the number of subjects who are randomised to the darbepoetin alfa 20090160 study and meet the entry criteria for the protocol. It is estimated that approximately 20% of the subjects that complete the double-blind treatment and active treatment periods of the darbepoetin alfa 20090160 study might be eligible to enroll; however, not all subjects may consent, nor will the majority of sites participate in the companion study.

10.3 Planned Analyses

No formal hypothesis will be tested. All study results will be descriptive. Treatment emergent adverse events, progression to AML and death will be summarised.

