Statistical Considerations: All study results will be descriptive, with no inferential tests. Treatment-emergent adverse events, progression to AML, and deaths will be summarized with descriptive statistics. Treatment-emergent adverse events will be summarised by system organ class and preferred term. Tables of fatal adverse events, serious adverse events, adverse events leading to withdrawal from IP and significant treatment-emergent adverse events will also be provided. For a full description of statistical analysis methods, please refer to Section 10.

Sponsor: Amgen Inc.

DES version/date

[figure not shown]
Version 3.0 31 January 2013

AMGEN[®]

Product: Darbepoetin alfa Synopsis Clinical Study Report: 20130113 Final Analysis Date: 27 June 2017

Product: Darbepoetin alfa Protocol Number: 20130113 Date: 01 April 2013

Study Design and Treatment Schema

AMGEN

Page 5 of 66

Page 6 of 66

Study Glossary

| Abbreviation or Term | Definition/Explanation |
|--|--|
| 5q- | MDS with isolated del(5q) |
| ACS | Acute coronary syndrome |
| AIDS | Acquired Immunodeficiency Syndrome |
| ALT | Alanine transaminase |
| AML | Acute myelogenous leukemia |
| ANC | Absolute neutrophil count |
| ASCO | American Society of Clinical Oncology |
| ASH | American Society of Hematology |
| AST | Aspartate aminotransferase |
| ATE | Arterial thromboembolic event |
| Baseline haemoglobin | Haemoglobin value measured on study day 1 (the day of first administration of IP) before administration of IP and assessed by the local laboratory |
| CI | Confidence interval |
| CMML | Chronic Myelomonocytic Leukemia |
| eCRF | Electronic case report form |
| CTCAE | Common Terminology Criteria for Adverse Events |
| DGHO | Deutsche Gesellschaft für Hämatologie und Onkologie (German Association for Haematology and Oncology) |
| DILI | Drug-induced liver injury |
| DVT | Deep vein thrombosis |
| End of study (EOS) | Subjects will not receive IP beyond week 73. The overall end of study will occur once all subjects enrolled and dosed with IP either withdraw from the study early, die, or complete the treatment period of the study. The end of study for an individual subject will occur either when the subject is withdrawn from the study, dies, or completes the final EOS visit. |

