10.4 Planned Methods of Analysis

No statistical inferential tests will be done. Incidence of treatment-emergent adverse events will be analyzed using the analysis set. Descriptive summary statistics will be provided for demographic data, cumulative doses, and patient disposition data. Important protocol deviations will be provided. Missing data will not be imputed. Data collected in the study will not be combined with 20090160 study data.

Subject incidence of all treatment emergent adverse events will be tabulated by system organ class and preferred term. Tables of fatal adverse events, serious adverse events, adverse events leading to withdrawal from IP and significant treatment emergent adverse events will also be provided.

The incidence and percentage of subjects who develop anti-darbepoetin alfa antibodies (binding and if positive, neutralizing) at any time will be tabulated.

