4.1.2 Analysis Methods

Total enrollment is projected to be less than 10 subjects from 1 country. Given the small population, no summary statistics (descriptive or otherwise) will be provided. Listings will be provided for patient disposition data, baseline demographics, baseline characteristics, IP administration, and important protocol deviations. Listings will also be generated for the primary endpoint of all treatment-emergent adverse events by system organ class and preferred term. In addition, listings will be provided, by system organ class and preferred term, of all fatal adverse events, serious adverse events, adverse events leading to withdrawal from IP and significant treatment emergent adverse events. Progression to AML will also be summarized in a listing.

Listings of subjects who develop anti-darbepoetin alfa antibodies (binding and if positive, neutralizing) at any time will also be provided.

Missing data will not be imputed. Data collected in the study will not be combined with Amgen 20090160 study data.

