5. LIST OF PLANNED TABLES, FIGURES, AND LISTINGS

The following listings will be provided:

- Listing of demographics and baseline characteristics including: enrollment date, sex, age at enrollment, height, weight, heart rate, temperature, blood pressure, and hemoglobin at enrollment
- Listing of treatment emergent adverse events and significant treatment emergent adverse events by system organ class and preferred term
- Listing of fatal adverse events by system organ class and preferred term
- Listing of serious adverse events by system organ class and preferred term
- Listing of adverse events leading to withdrawal from IP by system organ class and preferred term
- Listing of subjects that progressed to AML
- Listing of exposure to IP may include: the number of weeks of dosing, the total number of doses, the average weekly dose ($\mu\text{g}/\text{week}$), the average dose

administered ($\mu\text{g}/\text{dose}$), the cumulative dose administered (μg), the weight-adjusted average dose administered ($\mu\text{g}/\text{kg}/\text{dose}$), and the weight-adjusted cumulative dose administered ($\mu\text{g}/\text{kg}$)

- Listing of Important Protocol Deviations
- Listing of all RBC transfusions given on-study
- Listing of development of anti-darbepoetin alfa antibodies (binding and if positive, neutralizing) at any timepoint
- Listing of Thrombovascular Events including:
 - Arterial thromboembolic events [ATEs]: stroke; transient ischemic attack [TIA]; acute coronary syndromes [ACS]; other arterial thrombosis/embolism;
 - Venous thromboembolic events [VTEs]: deep vein thrombosis [DVT]; pulmonary embolism [PE]; and other venous thrombosis (excluding superficial venous thrombosis).

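### Does the SAP leave AML progression and death under-reported by naming no deaths listing, listing AML progressors only and omitting parent-study exposure?

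*Protocol*

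**What the plan says.** Protocol 10.3 says "Treatment emergent adverse events, progression to AML and death will be summarised". The synopsis, under Statistical Considerations, says "Treatment-emergent adverse events, progression to AML, and deaths will be summarized with descriptive statistics". Protocol 10.4 turns this into outputs: "Tables of fatal adverse events, serious adverse events, adverse events leading to withdrawal from IP" and significant treatment-emergent events. It names no separate table of all deaths or of AML. It also states that "Data collected in the study will not be combined with 20090160 study data".

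SAP 4.1.2 projects fewer than 10 subjects from one country and, for that reason, drops all summary statistics in favour of listings. "Listings will be provided for patient disposition data, baseline demographics, baseline characteristics, IP administration, and important protocol deviations". On AML, "Progression to AML will also be summarized in a listing". It repeats the separation from the parent study: "Data collected in the study will not be combined with Amgen 20090160 study data".

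SAP section 5 then itemises 11 listings. They include "Listing of fatal adverse events by system organ class and preferred term", a listing of subjects who progressed to AML, and an exposure listing for the investigational product. None is titled deaths, none is titled disposition, and none carries parent-study dosing.

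**The concern.** Set against protocol 10.3, the SAP seems to fall short on two of three named outcomes. With so few subjects and listings only, each subject's line is the whole result, so a missing line or column is not trivial.

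Three things could go wrong. A death that is not recorded as a fatal adverse event might be lost. An empty AML listing might be read as no AML when nobody looked: AML is defined by blast, cytogenetic and marrow criteria, and Table 5 of the protocol schedules none of these. And a study meant to describe longer-term use would show only its own treatment period, so an event could not be placed on total time on drug.

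**Working it through.** The plan states no sample size, power or error rate on this point, so there is no figure to reproduce. The check is mainly a comparison of sections.

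**Death**

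1. SAP 2.1 counts adverse events with onset from study day 1 to the end-of-study visit, and serious adverse events with onset from consent to 30 days after the last dose. A fatal event with onset in either period belongs in the fatal adverse event listing, whatever its cause. Withheld doses can lengthen the gap between last dose and the end-of-study visit, but this does not matter here, because the first period runs to the visit itself.
2. Protocol 9.1.1 tells investigators how to report a death from progression when there are no signs or symptoms, so such a death also receives an event term.
3. Protocol 8.2.1 and 8.2.2 both list death as a reason for removal, from treatment and from the study. The disposition listing in SAP 4.1.2 should therefore show deaths a second time.
4. What is left: after early withdrawal, survival status may be sought in public records (protocol 8.1 and 12.4). This is permitted, not required. A death known only that way has no named output apart from disposition.

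**AML**

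1. Protocol 6.2.1.2 has treatment stopped when the investigator determines progression to AML. A known case should therefore show in the AML listing and in disposition.
2. Protocol 9.1.1 bars the term disease progression as an event. It does not bar a diagnosis of AML, and 9.2.1 asks for the diagnosis when it is known.
3. Table 5 has 11 rows and none is a blast, marrow or cytogenetic assessment. That does not show AML goes unassessed. Inclusion criterion 102 keeps subjects in the parent study's long-term follow-up, which by protocol 2.3 comes after the parent active period and so appears to run alongside this study. The documents do not say what that follow-up measures.
4. An empty listing is quite possible. As an illustration, take 9 subjects, 73 weeks (73 / 52.18 = 1.40 years), a constant hazard, and Table 1 of the protocol (25% to AML by 9.4 years for low risk, 3.3 years for intermediate-1):
   - low risk: 1 − 0.75^(1.40/9.4) = 4.2%; expected cases 9 × 0.042 = 0.4; chance of none 0.958^9 = 0.68
   - intermediate-1: 1 − 0.75^(1.40/3.3) = 11.5%; expected cases 9 × 0.115 = 1.0; chance of none 0.885^9 = 0.33

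   Table 1 describes MDS patients by risk group, not subjects selected for a continuing response, so these are orders of magnitude only.

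**Parent-study exposure**

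Protocol 2.3 gives 24 double-blind and 48 active weeks in the parent study; protocol 3.5.1 gives about 73 weeks here. In nominal weeks for a completer:

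- randomised to darbepoetin: 24 + 48 + 73 = 145 weeks, of which 72/145 = 49.7% is not shown
- randomised to placebo, assuming a switch to darbepoetin in the active period: 48 + 73 = 121 weeks, of which 48/121 = 39.7% is not shown
- difference between two completers with identical lines: 145 − 121 = 24 weeks

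This is a real limit on interpretation. It is not a conflict between protocol and SAP: 10.3 does not mention prior exposure, and both documents rule out combining the data sets.

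**The case for a change.** The best argument for a change rests on AML. The SAP defines progression by criteria that this protocol does not schedule, and then lists only those who met them. A reader who sees an empty page cannot separate a subject who did not progress from one who was not assessed, and the illustration shows that an empty page is a likely outcome. A status entry for every subject would cost little. The exposure argument has some force too: the stated aim is longer-term safety, and showing the parent arm and prior dose as reference columns would not amount to pooling.

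Part of this stands. A row per subject with AML status, last follow-up and vital status would be tidier, and analysts with fewer than 10 subjects may well produce it. But it would not cure the weakness it points to. Without added procedures, many entries might simply read as not assessed. Who was enrolled, who stopped treatment and why can already be read from the demographics, disposition and exposure listings. Parent-study columns are an optional improvement that a sponsor may reasonably decline, having chosen to keep the data sets apart.

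The disposition listing is promised in SAP 4.1.2 and missing from section 5. That is a true inconsistency, but the commitment in 4.1.2 is plain enough to be followed.

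**Conclusion.** The observations are correct: 11 listings, none titled deaths or disposition, AML progressors only, no parent-study exposure. They do not call for a change. Followed as written, the plan would still report the known deaths and the known AML progressions, subject by subject, in a study too small for summary statistics. The omission of disposition from section 5 is clerical, the AML row is added detail that does not improve ascertainment, and the exposure boundary is a deliberate choice stated in both documents.

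The effect is confined to deaths found only through an optional record search and to the labelling of non-progressors among at most nine subjects. The documents do not allow the first group to be counted.

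This rests on three assumptions: that fatal events are reported as the protocol requires, that the disposition listing gives the reason for leaving treatment and study, and that enrolment stays near the SAP's projection. SAP section 1 also says the document covers analyses that are not for the clinical study report, so the commitment in protocol 10.3 may be met in a plan that is not among these documents; a breach cannot be established from what is here.

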10.4 Planned Methods of Analysis

No statistical inferential tests will be done. Incidence of treatment-emergent adverse events will be analyzed using the analysis set. Descriptive summary statistics will be provided for demographic data, cumulative doses, and patient disposition data. Important protocol deviations will be provided. Missing data will not be imputed. Data collected in the study will not be combined with 20090160 study data.

Subject incidence of all treatment emergent adverse events will be tabulated by system organ class and preferred term. Tables of fatal adverse events, serious adverse events, adverse events leading to withdrawal from IP and significant treatment emergent adverse events will also be provided.

The incidence and percentage of subjects who develop anti-darbepoetin alfa antibodies (binding and if positive, neutralizing) at any time will be tabulated.

11. REGULATORY OBLIGATIONS

11.1 Informed Consent

An initial sample informed consent form is provided for the investigator to prepare the informed consent document to be used at his or her site. Updates to the template are to be communicated formally in writing from the Amgen Clinical Study Manager to the investigator. The written informed consent document is to be prepared in the language(s) of the potential patient population.

Before a subject's participation in the clinical study, the investigator is responsible for obtaining written informed consent from the subject or legally acceptable representative after adequate explanation of the aims, methods, anticipated benefits, and potential hazards of the study and before any protocol specific screening procedures or any IP is administered. A legally acceptable representative is an individual or other body authorized under applicable law to consent, on behalf of a prospective subject, to the subject's participation in the clinical study.

The acquisition of informed consent and the subject's agreement or refusal of his/her notification of the primary care physician is to be documented in the subject's medical records, and the informed consent form is to be signed and personally dated by the subject or a legally acceptable representative and by the person who conducted the informed consent discussion. The original signed informed consent form is to be retained in accordance with institutional policy, and a copy of the signed consent form is to be provided to the subject or legally acceptable representative.

If a potential subject is illiterate or visually impaired and does not have a legally acceptable representative, the investigator must provide an impartial witness to read the informed consent form to the subject and must allow for questions. Thereafter, both the subject and the witness must sign the informed consent form to attest that informed consent was freely given and understood.

11.2 Independent Ethics Committee

A copy of the protocol, proposed informed consent form, other written subject information, and any proposed advertising material must be submitted to the IEC for written approval. A copy of the written approval of the protocol and informed consent form must be received by Amgen before recruitment of subjects into the study and shipment of Amgen investigational product.

The investigator must submit and, where necessary, obtain approval from the IEC for all subsequent protocol amendments and changes to the informed consent document. The investigator is to notify the IEC of deviations from the protocol or serious adverse events occurring at the site and other adverse event reports received from Amgen, in accordance with local procedures.

The investigator is responsible for obtaining annual renewal throughout the duration of the study. Copies of the investigator's reports and the IEC continuance of approval must be sent to Amgen.

11.3 Subject Confidentiality

The investigator must ensure that the subject's confidentiality is maintained for documents submitted to Amgen.

- Subjects are to be identified by a unique subject identification number.
- Where permitted, date of birth is to be documented and formatted in accordance with local laws and regulations.
- On the eCRF demographics page, in addition to the unique subject identification number, include the age at time of enrollment.
- For Serious Adverse Events reported to Amgen, subjects are to be identified by their unique subject identification number, initials (for faxed reports, in accordance with local laws and regulations), and date of birth (in accordance with local laws and regulations).
- Documents that are not submitted to Amgen (eg, signed informed consent forms) are to be kept in confidence by the investigator, except as described below.

In compliance with International Conference on Harmonisation (ICH) – Good Clinical Practices (GCP) Guidelines, it is required that the investigator and institution permit authorized representatives of the company, of the regulatory agency(s), and the IEC direct access to review the subject's original medical records for verification of study related procedures and data. Direct access includes examining, analyzing, verifying, and reproducing any records and reports that are important to the evaluation of the study. The investigator is obligated to inform and obtain the consent of the subject to

Page 45 of 66

Page 46 of 66

Product: Darbepoetin alfa Protocol Number: 20130113 Date: 15 April 2013

permit such individuals to have access to his/her study related records, including personal information.

11.4 Investigator Signatory Obligations

Each clinical study report is to be signed by the investigator or, in the case of

multi-center studies, the coordinating investigator.

The coordinating investigator, identified by Amgen, will be any or all of the following:

- a recognized expert in the therapeutic area
- an Investigator who provided significant contributions to either the design or interpretation of the study
- an Investigator contributing a high number of eligible subjects

12. ADMINISTRATIVE AND LEGAL OBLIGATIONS

12.1 Protocol Amendments and Study Termination

If Amgen amends the protocol, agreement from the Investigator must be obtained. The IEC must be informed of all amendments and give approval. The investigator **must** send a copy of the approval letter from the IEC to Amgen.

Amgen reserves the right to terminate the study at any time. Both Amgen and the Investigator reserve the right to terminate the Investigator's participation in the study according to the study contract. The investigator is to notify the IEC in writing of the study's completion or early termination and send a copy of the notification to Amgen.

Subjects may be eligible for continued treatment with Amgen investigational product by an extension protocol or as provided for by the local country's regulatory mechanism. However, Amgen reserves the unilateral right, at its sole discretion, to determine whether to supply Amgen investigational product and by what mechanism, after termination of the study and before the product is/are available commercially.

12.2 Study Documentation and Archive

The investigator is to maintain a list of appropriately qualified persons to whom he/she has delegated study duties. All persons authorized to make entries and/or corrections on eCRFs will be included on the Amgen Delegation of Authority Form.

Source documents are original documents, data, and records from which the subject's eCRF data are obtained. These include but are not limited to hospital records, clinical and office charts, laboratory and pharmacy records, diaries, microfiches, radiographs, and correspondence.

The Investigator and study staff are responsible for maintaining a comprehensive and centralized filing system of all study related (essential) documentation, suitable for inspection at any time by representatives from Amgen and/or applicable regulatory authorities.

Elements include:

- Subject files containing completed eCRFs, informed consent forms, and subject identification list
- Study files containing the protocol with all amendments, Investigator's Brochure, copies of prestudy documentation, and all correspondence to and from the IEC and Amgen
- Investigational product-related correspondence including Investigational Product Accountability Record(s), Return of Investigational Product for Destruction Form(s), Final Investigational Product Reconciliation Statement, as applicable.

In addition, all original source documents supporting entries in the eCRFs must be maintained and be readily available.

Retention of study documents will be governed by the Clinical Trial Agreement.

